We will recruit older Veterans with dysvascular LLA (1-5 years after LLA) to participate in the PABC intervention, which uses established VA Health Care system technology and evidence-based intervention methods. The five key dimensions of feasibility to be assessed are whether Veterans: 1) can successfully participate in the intervention (practicality), 2) tolerate physical activity progression (implementation feasibility), 3) are interested and enjoy the intervention (acceptability), 4) complete the intervention safely (safety), and 5) respond to the intervention with increased activity and decreased disability (responsiveness).^{31,32} Measures of physical activity and disability will be used to establish effect size estimates for the PABC intervention, with the intention of planning a future clinical efficacy trial. Testing will occur at baseline (pre-intervention), three months (end of intervention), and six months, using a two-group randomized crossover design.

Primary Aim: Determine feasibility of using the PABC intervention with older Veterans who have dysvascular LLA by assessing: 1) practicality (measured by retention rate), 2) implementation feasibility (measured by dose goal attainment), 3) participant acceptability (measured by the Intrinsic Motivation Inventory (IMI) – Interest / Enjoyment Subscale), and 4) safety (measured with Adverse and Serious Adverse Events).

Hypothesis 1.1: Retention rate will be at least 85% over the PABC intervention period (i.e., ≤15% attrition).

Hypothesis 1.2: At least 75% of participants will meet the dose goal of a 3% average increase in daily steps per week, across the three months of intervention.

Hypothesis 1.3: Participants will indicate PABC intervention acceptability with a mean score of ≥ 5/7 on the IMI – Interest / Enjoyment Subscale.

Hypothesis 1.4: There will be similar rates of study related (definitely, probably, possibly) adverse events between groups during the first three months (period of direct comparison of intervention versus control).

Secondary Aim: Establish effect size estimates of the PABC intervention (responsiveness)

using physical activity and self-report disability outcomes.

Hypothesis 2.1: The PABC group will have increased activity counts and less self-reported disability than the control group at Month 3, each with effect size estimates ≥ 0.80 (Cohen's d).

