The proposed pilot study is a randomized, tester-blinded design assessing PABC intervention feasibility (Aim 1) and effect size (Aim 2). Randomization ($n=32$) will create two groups (GROUP1 or GROUP2) using computer-generated random blocks of 2 and 4, stratified by amputation level (transtibial and transfemoral). An investigator not involved with testing or intervention ([name]) will conceal group allocation. A crossover design is used to simultaneously accomplish the aims and optimize recruitment (Fig.2). The PABC Intervention will be delivered to both groups (GROUP1 during Months 1-3 and GROUP2 during Months 4-6). The crossover design provides $n=32$ for assessing Aims 1 and 2. Intervention effect retention will be tested at six months for GROUP1 ($n=16$).

D.1. Setting

The study will occur at the VA Geriatric Research Education and Clinical Center (GRECC), where Drs. [name] and [name] have dedicated positions ([name] (GRECC Director)). Intervention delivery will occur with the participant at home and therapist at a VA site with access to tablet interface software (e.g. VA Jewell Motion Analysis Lab or VA Clinical Building South, using VA-supplied and approved mobile-health tablets and wearable activity sensors (FitBit)).

D.2. Participants

Thirty-two participants will be recruited from the Denver VAMC. The target sample is older Veterans diagnosed with PAD and/or DM, who have major LLA. We expect $<15\%$ attrition, with a goal of 26 participants completing.

D.3. Eligibility Criteria

Inclusion criteria: ≥ 50 years of age, LLA 1-5 years prior, Type II DM and/or PAD, and

ambulatory without human assistance, in the home or better using a prosthesis, with assistive device as needed, with assistive device as needed. Exclusion criteria: wheelchair as primary form of locomotion, trauma or cancer-related etiology of the LLA, unstable heart condition, uncontrolled hypertension, acute systemic infection, cancer, recent stroke (within 2 years), or lower extremity wound or ulcer that limits ambulation.

D.4. Recruitment Strategies

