The FitBit sensor will be used to guide the intervention and data from the sensors will NOT include personal health information; with generic accounts will be created for each user without participant-identifiable information. FitBit data will not be used as outcomes, but rather, only to guide the PABC intervention. Outcome data will be managed using the REDCap (Research Electronic Data Capture) platform. REDCap is a secure, web-based application designed to support research data capture, providing user-friendly case report forms, real-time data entry validation (e.g., data type and range checks), audit trails, transaction logs, and a de-identified data export to common statistical packages. The VA Eastern Colorado Health Care System has approved REDCap for research use. More detail is provided in the Human Subjects section.

D.8. Sample Size Estimate

The sample size estimate was based on evidence for activity change in patients with DM and PAD, which indicates a reasonable expected increase of 3% walking activity per week (e.g., steps, distance, time) over 3 months.^{3, 12, 77, 78} A baseline mean (SD) of 2000 (900) steps/day was estimated based on data from our ongoing dysvascular LLA RCT (Section C.3.) and published LLA data.^{49, 79, 80} A 3% weekly increase in steps during intervention, assuming no order effect, would provide an effect size of 0.8 (Cohen's d). Based on those assumptions, a sample size of 13 per group with a crossover design (total n=26) provides >95% power to detect an intervention effect (effect size=0.8, $\alpha=0.05$, two-tailed paired t test). The study is generously powered intentionally, because the assumption of 'no order effect' will not likely hold. We will recruit 32 participants, and expect at least 26 to complete. This 15% attrition estimate is conservative, based on an historical attrition rate <15% in our intervention studies with other older adult populations^{81, 82} and our current dysvascular LLA RCT.

D.9. Data Analysis Plan

Aim 1 (Feasibility of PABC Intervention): The analyses for Aim 1 are based on four hypotheses: H1.1) participant retention, H1.2) dose goal attainment, H1.3) intervention acceptability, and H1.4) safety.

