- H1.1) Retention rate will be assessed using a cut off of 15% attrition (i.e., loss of >6 participants). Mean attrition rate will be compared to the null value of 15% using a one-sample t-test ($\alpha=0.05$). This attrition rate is considered feasible based on previous activity change programs for patients with DM or PAD.^{5, 83}
- H1.2) Dose goal attainment will be assessed by the proportion of participants achieving the goal of 3% average weekly increase in steps, based on activity gains in other intervention studies.^{3, 12, 78} The ability to attain a 3% average weekly step increase for <75% of the participants will be considered a negative result. The proportion of participants attaining a 3% average weekly step increase will be reported (95% CI) and compared to the null value of 75% using a one-sample binomial proportions test ($\alpha=0.05$).
- H1.3) Acceptability of the intervention will be measured with the IMI Interest and Enjoyment subscale, with a mean score of <5/7 considered a negative acceptability result.¹⁰ Mean IMI Interest and Enjoyment score will be compared to the null value of 5.0 using a one-sample t-test ($\alpha=0.05$).
- H1.4) Adverse and serious adverse event (AE/SAE) rates (events/participant) will be compared between groups for Months1-3 (PABC intervention for GROUP1, attention control for GROUP2). We expect similar AE/SAE rates between groups (assessed by Safety Officer and research team).

Aim 2 (Effect Size and Preliminary Efficacy of PABC Intervention): Effect size of the PABC intervention will be calculated with Cohen's d using mean and standard deviation for change in activity counts and LLFDI scores. Statistical inference of group differences for calculation of sample size estimates will be based on linear models with activity counts and LLFDI scores as outcome variables. Explanatory variables in each model will include primary medical diagnosis (PAD, DM, or both), group, and baseline activity count or LLFDI score.

D.10. Expected Outcomes and Interpretation

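### The power above 95% in section D.8 is for a paired t test on 26 people, not for the between-group Month 3 comparison in H2.1 and D.9, and D.8 does not say which SD its d of 0.8 uses

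*Combined protocol and SAP*

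**What the plan says.** - **D.8 (Sample Size Estimate)** assumes a baseline mean (SD) of 2000 (900) steps/day and a 3% weekly increase over 3 months, and converts these to d = 0.8. It then says that "a sample size of 13 per group with a crossover design (total n=26) provides >95% power to detect an intervention effect", for a two-tailed paired t test at alpha 0.05. It calls the study generously powered because it does not expect the absence of an order effect to hold.
- **Section A, Hypothesis 2.1**: "The PABC group will have increased activity counts and less self-reported disability than the control group at Month 3", each with an effect size of at least 0.80. Hypothesis 1.4 describes the first three months as the "period of direct comparison of intervention versus control".
- **D.9, Aim 2**: "Statistical inference of group differences for calculation of sample size estimates will be based on linear models". The covariates are listed: "Explanatory variables in each model will include primary medical diagnosis (PAD, DM, or both), group, and baseline activity count or LLFDI score". No time point, paired test, or period, sequence or subject term is given. The effect size is defined separately: "Effect size of the PABC intervention will be calculated with Cohen's d using mean and standard deviation for change in activity counts" and LLFDI scores.
- **Section D, opening paragraph**: "The crossover design provides $n=32$ for assessing Aims 1 and 2". It adds that "Intervention effect retention will be tested at six months for GROUP1".
- **D.5**: GROUP2 has the attention control in Months 1-3. GROUP1 has a no-contact wash-out in Months 4-6.

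**The concern.** The power statement and the analysis describe different comparisons. A paired t test on 26 people needs each person to supply both a PABC and a control measurement. GROUP1 never has the attention control: its second period is untreated follow-up, used to see whether the effect lasts. The PABC-versus-control pair therefore exists only within GROUP2, where control always comes first and treatment is confounded with period. A pre-to-post change over each person's PABC period can be pooled over both groups and is paired, and it may be what D.8 had in mind. But it has no control and cannot test H2.1.

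A second gap makes the first harder to repair. D.8 does not name the SD behind 0.8, D.9 uses the SD of change, and no correlation between baseline and Month 3 is given. The power of the planned comparison depends on both.

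The estimates are meant to size a later efficacy trial. A reader who takes the D.8 figure as describing the Month 3 contrast will think that contrast more precise than it is.

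**Working it through.** **Inputs.** From D.8: d = 0.8, two-sided alpha 0.05, 26 completers (13 per group), 32 recruited (16 per group), baseline 2000 (900) steps/day, 3% per week. From D.5: 12 weekly visits. From D.9: a model with group, baseline value and a three-level diagnosis, so 5 parameters and df = 2n − 5 with n per group. Assumed: the baseline-to-Month-3 correlation r (not stated, so a range is shown) and equal SDs at the two times.

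**1. D.8's own figure.** Paired t, noncentrality 0.8 × √26 = 4.08, df 25: power **97.5%**. The statement holds for the test it names, if 0.8 is on the SD of the paired differences.

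**2. Where 0.8 may come from.** 0.03 × 12 × 2000 = 720 steps, and 720/900 = 0.80. This is a reconstruction that assumes 12 weeks without compounding. With compounding, 2000 × (1.03^12 − 1)/900 = 0.95. The match suggests the baseline SD. If so, the paired standardised difference is 0.8/√(2(1 − r)), which equals 0.8 only at r = 0.5. Paired power with 26 is then 79% at r = 0, 91% at 0.3, 97.5% at 0.5 and 99.9% at 0.7, and it passes 95% only from r of about 0.41.

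**3. Power of the D.9 group comparison (noncentral t, df = 2n − 5).**

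- Reading A, 0.8 on the baseline SD: noncentrality = 0.8/√(1 − r²) × √(n/2).
- Reading B, 0.8 on the SD of change: noncentrality = 0.8 × √(2(1 − r))/√(1 − r²) × √(n/2).

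Example, n = 13, r = 0.5: both give 0.924 × 2.550 = 2.355, df 21, power 61%.

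| r | A, 13 v 13 | A, 16 v 16 | B, 13 v 13 | B, 16 v 16 |
|---|---|---|---|---|
| 0 | 49% | 59% | 79% | 87% |
| 0.3 | 53% | 63% | 67% | 77% |
| 0.5 | 61% | 71% | 61% | 71% |
| 0.7 | 78% | 86% | 56% | 66% |
| 0.8 | 90% | 95% | 54% | 63% |
| 0.9 | 99% | >99% | 52% | 61% |

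Under A, 95% needs r of about 0.84 (13 v 13) or 0.80 (16 v 16). Under B the maximum over this range is at r = 0, so 95% is not reached.

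**4. Simulation of the D.9 model** (300,000 runs per cell; diagnosis drawn at random from three equally common categories with no effect on outcome, which is an assumption). At r = 0.3, 0.5, 0.7, 0.8:

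- A: 48%, 56%, 72%, 86% (13 v 13) and 58%, 67%, 83%, 93% (16 v 16). Power of 95% needs r of about 0.87 or 0.82.
- B: 62%, 56%, 51%, 49% and 73%, 67%, 61%, 59%. The maximum, at r = 0, is 73% and 83%.

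Simulated power is lower because chance imbalance in the covariates costs some precision.

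**5. The paired contrast that does exist (GROUP2 only).** With 0.8 on the SD of paired differences, noncentrality 0.8 × √13 = 2.88 gives 75%, and 0.8 × √16 = 3.20 gives 85%.

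**6. Precision of an observed d of 0.8.** Unadjusted 95% CI, by inverting the noncentral t: −0.01 to 1.59 (13 v 13) and 0.07 to 1.52 (16 v 16). Baseline-adjusted on the baseline SD, 0.8 ± t(2n − 5) × √(2(1 − r²)/n), with 13 v 13: 0.09 to 1.51 at r = 0.5 and 0.31 to 1.29 at r = 0.8.

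**The case against.** The strongest reply is that D.8 is open about its method. It names the test, the sample size, d and alpha, warns about the order effect, and never claims to give the power of H2.1. On this view the defect is a missing link between sections. That is fair as a description, but D.9 contains no paired analysis for the figure to belong to, and the margin D.8 offers is tied to the order effect, not to a change of test.

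Second, Reading B moves the number 0.8 to another SD. If the 720 steps and SD of 900 are held fixed, the D.9 model has the power in Reading A whichever way d is later expressed. This stands: the result that 95% is never reached applies to 0.8 on the SD of change, which is D.9's definition and so the one behind H2.1's threshold. It does not show that a 720-step effect would be missed. Likewise, under Reading A the paired comparator is 97.5% only at r = 0.5.

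Third, baseline adjustment can rescue the power. At r = 0.9, Reading A gives 99% or more. That is true, but the plan states no r, so the reader cannot know whether it applies.

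Fourth, this is a pilot, H2.1 has no significance rule, and H2.2 sizes the later trial from observed means and SDs. This limits the consequence, but it does not make the stated power correct for the planned comparison.

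**Conclusion.** The concern holds. The D.8 calculation is right for the test it names, but that test is not the H2.1/D.9 comparison and cannot be carried out as PABC versus control on all 26 people. With 13 v 13, closed-form power of the planned comparison is 53% to 90% for r from 0.3 to 0.8 on the baseline SD, and 79% falling to 52% for r from 0 to 0.9 on the SD of change. With 16 v 16 the ranges are 63% to 95% and 87% falling to 61%. Simulation under the assumed diagnosis mix gives figures a few points lower. No single corrected power follows, because the SD and r are not stated. A flat 50% (the unadjusted two-sample figure for 13 v 13) would overstate the problem, since D.9 adjusts for baseline.

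This should be fixed but is not critical. Aim 2 is secondary, and neither the primary feasibility aim nor the sample size has to change. All figures assume equal SDs at both times and treat steps/day as a stand-in for activity counts. They say nothing about LLFDI.

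**What to change.** In this order:

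1. Name the Aim 2 contrast (between groups, Month 3) and one SD for Cohen's d, baseline or change, and use it in D.8, H2.1 and D.9.
2. In D.8, replace the paired-test power and the remark about generous power with the power of the D.9 Month 3 comparison on the chosen SD, for 13 and 16 per group over a stated range of r, preferably from simulating the D.9 model. Say that it is computed in steps/day as a proxy for activity counts and does not cover LLFDI. If the paired figure is kept, label it as the pooled, uncontrolled pre-to-post PABC change, not a test of H2.1, and name its SD.
3. In the opening of section D, limit n = 32 to outcomes pooled over the PABC periods, and state 16 v 16 randomised for H2.1. The H1.4 safety comparison over Months 1-3 has the same 16 v 16 basis and could be noted there.
4. In D.9, state the time point and report the Month 3 between-group d with a 95% CI, saying whether it is unadjusted or baseline-adjusted.

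The cost is protocol wording only: no extra participants, visits or data. The stated power for a secondary aim becomes less favourable, which is acceptable in a pilot.

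### H1.1 equates a 15% attrition cut-off with losing more than 6 participants, but with 32 participants 15% is passed at 5 losses, so 5 or 6 losses give opposite verdicts

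*Combined protocol and SAP*

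**What the plan says.** Section A, Hypothesis 1.1, sets the pass mark as a percentage: "Retention rate will be at least 85% over the PABC intervention period (i.e., ≤15% attrition". Section D.9, H1.1, repeats the percentage and adds a count: "Retention rate will be assessed using a cut off of 15% attrition (i.e., loss of >6 participants". It then names a test: "Mean attrition rate will be compared to the null value of 15% using a one-sample t-test", at α = 0.05 with no sidedness given.

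The opening of section D supplies the denominator: "The crossover design provides $n=32$ for assessing Aims 1 and 2".

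Two other places link 15% to 26 completers. Section D.2: "We expect $<15\%$ attrition, with a goal of 26 participants completing". Section D.8: "We will recruit 32 participants, and expect at least 26 to complete. This 15% attrition estimate is conservative". The 26 is the number used in the power statement: "a sample size of 13 per group with a crossover design (total n=26) provides >95% power".

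**The concern.** A parenthesis introduced by *i.e.* should restate the criterion, and this one sets a different and looser threshold. Retention is the first of the four feasibility criteria of the primary aim. With 5 or 6 losses, one reader could report it as met from the count and another as not met from the percentage, and the choice could be made after the result is known.

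H1.2 and H1.3 each say what will be taken as a negative result; for H1.2 it is "The ability to attain a 3% average weekly step increase for <75% of the participants will be considered a negative result". H1.1 has no such sentence, so the verdict depends on the cut-off, which is stated in two incompatible ways.

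A minor, separate point concerns the test. Attrition is yes or no for each person, yet H1.1 uses a one-sample t-test where H1.2 uses a binomial test for the same kind of data.

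**Working it through.** **Inputs.** Cut-off 15% (section A, Hypothesis 1.1; section D.9, H1.1). Count: more than 6 (D.9, H1.1). Denominator 32 (opening of section D). Completers 26 (D.2, D.8). Losses so far in the team's ongoing amputation trial: 1 of 23 (C.3).

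**Can the plan's count be reproduced?** 0.15 × 32 = 4.8, so attrition above 15% means 5 or more losses. Equivalently, 0.85 × 32 = 27.2, so at least 28 must be retained; 27/32 = 84.4% falls short.

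| Losses of 32 | Attrition | Within 15%? | Within the count (not more than 6)? |
|---|---|---|---|
| 4 | 12.5% | yes | yes |
| 5 | 15.6% | no | yes |
| 6 | 18.75% | no | yes |
| 7 | 21.9% | no | no |

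Other readings do not produce the plan's figure:
- More than 6 is the same as more than 15% only if 6/n ≤ 0.15 < 7/n, which holds for n = 40 to 46. The documents give no such denominator.
- If some GROUP2 members leave before Month 4, the denominator for the PABC period falls below 32. For 27 to 31 participants 15% is still passed at 5 losses, and for 26 (0.15 × 26 = 3.9) at 4. The gap stays or widens.
- Reading the count as 6 or more still leaves 5 losses in conflict.

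**Likely source.** 32 − 26 = 6, but 6/32 = 18.75%. An allowance of 15% on 26 completers would need 26/0.85 = 30.6, that is 31 enrolled.

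**Does the planned test decide it?** p-values against 15%, n = 32, given as two-sided / one-sided for lower attrition / one-sided for higher attrition:
- 5 losses: t-test 0.924 / 0.538 / 0.462; exact binomial 0.808 / 0.654 / 0.536.
- 6 losses: t-test 0.597 / 0.702 / 0.298; exact binomial 0.618 / 0.805 / 0.346.

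None is significant; the smallest is 0.298.

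**How likely are 5 or 6 losses?** Losses ~ Binomial(32, p), with p assumed:

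| True attrition p | P(≤4) | P(≤6) | P(5 or 6) |
|---|---|---|---|
| 1/23 = 4.3% | 0.988 | 0.9996 | 0.011 |
| 10% | 0.789 | 0.964 | 0.176 |
| 15% | 0.464 | 0.805 | 0.341 |
| 20% | 0.204 | 0.535 | 0.331 |

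The exact 95% confidence interval for 1 of 23 is 0.1% to 21.9%, so that figure excludes none of these rates.

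**Minor point, the t-test.** With 0 losses the sample variance is zero and the t statistic is undefined. The chance of that is 24% at p = 1/23, 3.4% at 10% and 0.6% at 15%. At 1 loss the t-test gives two-sided p = 0.0006 and the exact test 0.078, so the choice of test can change the result.

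**The case against.** The best defence is that the percentage plainly governs. It is the hypothesis in section A, the cut-off in D.9 and the null value of the test. The count appears once, in a parenthesis, and no formula uses it. Any report would show the observed rate, so a reader could apply 15% directly. This is a good reason to resolve the conflict in favour of the percentage. It does not remove the conflict, because the count is part of the sentence that defines the criterion and agrees with the 26-completer goal stated elsewhere.

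A second objection is that 26 completers and retention over the PABC period measure different things. Completion also covers GROUP2's control months and GROUP1's no-contact months, so 26 completers can coexist with at least 85% retention during PABC. That is correct. The completion goal fails the 85% mark (26/32 = 81.25%) only if all 6 losses fall in the PABC period. What remains is that D.8 calls 26 of 32 a 15% attrition estimate, which it is not.

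Third, the larger probabilities need true attrition of 15% to 20%, while the plan expects less than 15%. At the 1-of-23 rate the chance is 1%. This is fair, but that rate is interim, comes from a different intervention and is imprecise.

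Fourth, a corrected count would be wrong again if the denominator changed; with 26 participants 15% is passed at 4 losses. The count should therefore be tied to 32, with the percentage governing otherwise.

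**Conclusion.** The concern holds. The count in H1.1 is wrong as written for a 15% cut-off with 32 participants: it should change the verdict at 5 losses and does so only at 7. The two stated rules give opposite verdicts at exactly two outcomes, 5 and 6 losses, and the planned test cannot separate them.

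The arithmetic rests only on the denominator of 32, and a smaller denominator does not help the plan. The 18% to 34% chance of landing on those outcomes assumes independent losses with a common rate of 10% to 20% and all 32 at risk; at 4.3% the chance is 1%. Because this is a pass/fail threshold on the first criterion of the primary aim, it needs correcting before data are seen. The choice of test and its unstated sidedness are minor; sidedness is equally unstated in H1.2 and H1.3.

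**What to change.** In D.9, H1.1, replace the parenthesis with: *(i.e., loss of >4 of 32 participants)*. Add: *Observed attrition of more than 15% over the PABC intervention period will be considered a negative result.* Name the denominator, and state that the percentage governs if it is not 32.

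If the sponsor does mean to tolerate 6 losses, the criterion should instead be restated as 18.75% attrition (81.25% retention) in both section A and D.9, before data are seen.

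In D.2 and D.8, describe 26 of 32 as an 18.75% allowance. The recruitment target need not change, since 15% attrition would require only 31.

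As a minor change, replace the t-test with an exact binomial test against 15% and an exact 95% confidence interval, as supporting information beside the observed cut-off, and state the sidedness. At the 5% level the exact test favours the plan only at 0 losses two-sided (p = 0.011; at 1 loss p = 0.078), or at 0 or 1 one-sided (at 1 loss p = 0.037; at 2 losses p = 0.122), so it should not carry the verdict.

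The cost is a few sentences, with no new data. The price is a stricter bar than the present count: the chance of passing falls from 96% to 79% if true attrition is 10%, and from above 99.9% to 98.8% at the 1-of-23 rate.
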